1.0 SUMMARY

This is a prospective, randomized, longitudinal study of the clinical outcomes of osteoarthritis patients treated by two different alignment philosophies for total knee replacement. Participants will be treated using the Stryker Triathlon® Total Knee System for Total Knee Arthroplasty (TKA) implanted using either Stryker OtisMed® ShapeMatch® Technology (intervention) or Stryker PrecisioN v4.0 Knee Navigation (control). Health status and functional outcome measures will be recorded to quantify functional status of subjects before surgery and at each follow-up interval. An economics analysis will also be conducted to compare costs associated with each technology platform.

There will be 2 sites (North Shore Hospital, Auckland and Waitakere Hospital, Waitakere), 1 Principal Investigator and 6 co-Investigators for this study. A maximum of 50 cases will be enrolled in each group, for a total of 100 patients. It is expected that participants will be recruited over a 6 month period. Total duration of the study is expected to be 1.5 years.

The study consists of two groups:

- 1. Intervention Group: Treatment by total knee replacement with a target lower limb alignment determined using pre-operative imaging and kinematic alignment, implemented using Stryker OtisMed® ShapeMatch® Technology:
- 2. Control Group: Treatment by total knee replacement with a target lower limb alignment equal to neutral Mechanical Axis, implemented using Stryker Knee Navigation.

Pre-operatively, all participants will be required to undergo medical imaging assessment using Magnetic Resonance Imaging (MRI) of the affected lower limb. These images will then be used to manufacture the patient-specific cutting guides for preparation of the bones prior to implantation of the total knee replacement.

All participants (control and intervention groups) will be requested to attend visits preoperatively and post-operatively at 6 weeks, 6 months and 12 months. At these visits participants will complete assessments relating to quality of life, pain and functional outcome. In addition, participants will have standard knee X-rays taken preoperatively and post-operatively. A post-operative CT scan will be obtained for all participants in order to assess implant position and orientation.

All devices used in this study have been registered with MedSafe NZ and are approved for sale and use in New Zealand.

This study will adhere to all relevant requirement and guidelines in relation to the conduct of clinical trials, including the Declaration of Helsinki (Appendix 5) and ICH Good Clinical Practice Guidelines, as implemented in New Zealand (Appendix 6).

An Extension Study will be undertaken to follow all patients (intervention and control group) who consent to continued follow-up. These patients will be followed out to 5 years post-surgery, with a follow up visit at 2 years and 5 years, to collect longer term data on radiographic and patient outcomes. Data will also be captured on the secondary objectives of revision rate, device-related adverse events and re-operation rates.

Visit Windows

Definition – Since it is not always possible for subjects to come in for a study visit on the exact date, most protocols allow a certain time period before or after the calendar date; this is known as the visit window. If a subject is not seen during the visit window, that visit will be regarded as a missed visit. Visit windows are calculated in reference to the baseline date, which is the surgery date (intra-op) for this study.

Patient Evaluation Schedule for All Patients

EVALUATION	History/ Pre-Op	Intra-Op	6 week	3 MO*	6МО	12MO
Demographics	√			-		
Medical History	✓					
MRI	√					
Surgical Details		√				
Oxford Knee Score	√		✓		√	✓
IKSS	✓		✓		✓	✓
FJS-12			✓		✓	√
WOMAC	√		✓		✓	√
EQ-5D-3L	✓		✓		✓	✓
VAS Pain	√		✓		✓	√
AP and ML X-rays	✓		✓			√
Perth CT Protocol				✓		

^{*3} month patient visit is non-standard, i.e. in addition to the usual follow-up routine for TKA patients.

The visit windows for this study are:

- Pre-Op = Within 2 months before the date of surgery
- Intra-op = Baseline time point
- 6 Weeks = +/- 2 weeks
- 3 Months = +/- 6 weeks (no patient visit CT scan only)
- 6 Months = +/- 1 month
- 12 Months = +/- 2 months

Extension Phase

EVALUATION	2 year	5 year
	follow-up	follow-up
Demographics	√	
Medical History	✓	
and Surgical		
Details Review		
Oxford Knee Score	1	✓
IKSS	1	✓
FJS-12	✓	/
WOMAC	✓	/
EQ-5D-3L	✓	✓
VAS Pain	√	/
AP and ML X-rays	✓	1
Long-leg weight- bearing x-rays	√	~

The visit windows for this study are:

- 2 years = +/- 6 months
- 5 years = +/- 6 months

2.0 INTRODUCTION

Total Knee Replacement (TKR) has evolved to a point where implant design combined with instrumentation and surgeon skill results in excellent implant survival. The New Zealand National Joint Register reported over 6000 knee replacements performed in New Zealand in 2009, with annual figures increasing over the last 10 years.

Total Knee Replacements are undertaken to treat a range of conditions including osteoarthritis, rheumatoid arthritis, avascular necrosis and secondary arthritis resulting from trauma.

Current surgical techniques make use of generic, re-usable instrumentation, consisting of intra- and/or extra-medullary rods on the femur and tibia to determine alignment in relation to anatomical landmarks, combined with bone resection guides

which ultimately determine position and orientation of the definitive implant components.

Traditionally, the goal of TKR has been to position the components such that the post-operative alignment goal is a straight limb, or a mechanical axis of 0° (Insall & Scott, 2001). The mechanical axis is defined by lines joining the centre of the femoral head, centre of the knee joint and the centre of the ankle. Despite the best efforts of the surgeon, the resulting limb alignment varies away from 0° by a small amount (typically less than ±3° in 80% of cases).

More recently, the use of computer navigation systems has been introduced to surgical practice with the aim of improving the ability to obtain post-operative limb alignment as close as possible to 0° (Chauhan et al, 2004).

Whilst achievement of neutral limb alignment has been considered desirable from an engineering point-of-view – to maximize implant longevity through minimizing the deleterious effects of polyethylene insert wear and particle-induced osteolysis and implant loosening – patient satisfaction of TKR has not always been ideal. Despite surgery being performed technically correct by surgeons, up to 1 in 5 patients express dissatisfaction in the functional result (Bourne et al, 2009). Patient expectations after surgery are also increasing due in part to the adoption of more active lifestyles amongst total knee replacement recipients where return to function can be of primary importance.

The opportunity exists to provide an alternative approach to TKR surgery which may result in improved patient outcomes. One such approach is to determine the optimal placement of components based on the individual anatomy of patients, rather than a generic limb alignment philosophy (Coughlin et al, 2003; Eckhoff et al, 2005). This approach relies on the creation of a pre-arthritic model of the bone and cartilage structures of the knee. A single, 3-D axis of rotation is then determined which takes into account the 3-D shape and orientation of the femoral condyles during the weight-bearing portion of gait. This is in contrast to traditional surgical techniques which set femoral component orientation and position using one or more of the transepicondylar axis, posterior-condylar axis and/or the anterior-posterior (or Whiteside's)

line. This new axis is then the basis of determining the so-called natural alignment goal for the joint replacement procedure.

A comprehensive three-dimensional description of the anatomy can be obtained by magnetic resonance imaging (MRI) scans obtained pre-operatively. Through a proprietary process, it is possible to pre-operatively develop a model of the arthritic bone and cartilage, adapt that model to take into account degenerative process, and generate a model of the pre-arthritic anatomy (Fig. 1). The pre-arthritic state then becomes the surgical goal in terms of limb alignment. Custom cutting guides are generated for each individual patient to enable the surgeon to perform the bone resections in such a way that the resultant construct with the TKR components reproduces the pre-disease limb alignment (Fig. 2). Early experience of applying this technique indicates that patient outcomes and function assessed during the early post—operative phase are superior to conventional approaches to TKR (Howell et al, 2008; Spencer et al, 2009). Other potential advantages of this technology include a reduction in blood loss (as no intramedullary rod is used), and a reduction in ligament releases (as the total knee components effectively resurface the knee with restoration of the natural alignment) (Howell et al, 2008).

[figure not shown]
[figure not shown]

Figure 1: Workflow and data transfer process used for preparation of ShapeMatch® cutting guides.

Figure 2: Intra-operative image of ShapeMatch[®] cutting guides positioned on distal femur and proximal tibia. Femoral cutting guide has been pinned in place, ready for bone resection. Tibial cutting guide being positioned prior to pinning.

A consecutive cohort study is underway in Australia to test this reproducibility in osteoarthritic patients and to further follow the patient outcome to 6 months following surgery with ShapeMatch[®] cutting guides.

This protocol outlines a randomized controlled study for the comparison of this new approach, the use of ShapeMatch® cutting guides, to the conventional approach to total knee replacement currently used as the standard of care by the Investigators.

Following on from this study, an extension study will be undertaken to determine the clinical and radiographic outcomes out to 5 years post-surgery.

3.0 OBJECTIVES

The primary objective of this study is:

• To demonstrate, through calculation of Oxford Knee Score at 12 months postoperative, that total knee replacement (TKR) performed using the ShapeMatch® Cutting Guide provides improvement from preoperative levels of patient pain and function comparable to the improvement obtained with TKR performed using computer-assisted Navigation. Oxford Knee Scores will be calculated pre-operatively and at 6 weeks, 6 months and 12 months post-operatively.

The secondary objectives of this study are:

- The efficacy objective is to compare radiographic, pain, function and health-related quality of life (QOL) between the ShapeMatch® Cutting Guide group and the computer-assisted Navigation control group. This objective will be achieved by utilizing the following instruments pre-operatively and at the 6-week, 6-month and 12 month visits:
 - Perth CT protocol
 - AP and ML X-rays
 - Oxford Knee Score
 - The International Knee Society Score (IKSS)

- The Forgotten Joint Score (FJS-12)
- WOMAC
- EQ-5D-3L
- VAS Pain
- To compare the cost-effectiveness and cost-utility of the procedure between the ShapeMatch[®] Cutting Guide group and the computer-assisted Navigation control group. This objective will be assessed by recording and calculating the following parameters:
 - o Wound length
 - Total duration of operating procedure (anaesthetic time and skinto-skin incision time)
 - o Cost of consumable items used during operating procedure
 - Length of stay in hospital
 - o Quality-adjusted life-years (QALYs) from EQ-5D-3L

The hypothesis is that there is a statistically significant improvement in functional outcome 12 months following a primary Total Knee Replacement when kinematic limb alignment (using ShapeMatch® Cutting Guide) is used compared to that resulting from a goal of neutral mechanical axis alignment (using computer-assisted Navigation).

The Extension Study Primary Objective is:

To determine the clinical and radiographic outcomes at 2 years and 5 years post-surgery, in patients receiving a Stryker Triathlon[®] Total Knee System for Total Knee Arthroplasty (TKA) implanted using either Stryker OtisMed[®] ShapeMatch[®] Technology (intervention) or Stryker PrecisioN v4.0 Knee Navigation (control).

The Extension Study Secondary Objectives are:

 To determine the revision rate, device-related adverse events and reoperation rates.

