12.0 STATISTICAL METHODS

12.1 Sample Size Justification

The New Zealand National Joint Registry reported a mean Oxford Knee Score of 37.05 (with a standard deviation of 8.30) at 6 months following total knee arthroplasty, using mostly conventional instruments (NZOA New Zealand Joint Registry, 2010). The registry also reports the following scoring categories: Excellent >41, Good 34-41, Fair 27-33, and Poor <27.

Kamat et al. (2009) undertook a study comparing the clinical outcomes of manual versus computer-assisted surgery instrumentations systems. A 5-point change in Oxford Knee Scores at a post-operative period of 6 months was determined to be a clinically meaningful difference.

A minimum of 45 patients per group are required, based on an improvement from 37 (mean Oxford Knee Score reported in the New Zealand registry) to 42 (scoring category of excellent), with 80% power and significance level of 5%.

An additional 5 patients per group (10%) has been included into the target patient number to allow for loss to follow-up, bringing the target to 50 patients per group.

A maximum of 100 patients will be enrolled in the Extension Study.

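### The primary objective is to show comparable improvement, the hypothesis is superiority, and no margin or decision rule links the confidence interval to either

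*Combined protocol and SAP*

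**What the plan says.** Four places bear on what the trial is meant to show.

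- **3.0 Objectives, primary objective.** The trial is to demonstrate that ShapeMatch "provides improvement from preoperative levels of patient pain and function comparable to the improvement obtained with TKR performed using computer-assisted Navigation", judged on the Oxford Knee Score at 12 months.
- **3.0 Objectives, hypothesis.** "The hypothesis is that there is a statistically significant improvement in functional outcome 12 months following a primary Total Knee Replacement" with kinematic alignment, compared with a neutral mechanical axis target. The Introduction (2.0) has the same aim: "The opportunity exists to provide an alternative approach to TKR surgery which may result in improved patient outcomes".
- **12.1 Sample Size Justification.** "A minimum of 45 patients per group are required, based on an improvement from 37" (the registry mean) "to 42 (scoring category of excellent), with 80% power and significance level of 5" percent. The variability input is a "mean Oxford Knee Score of 37.05 (with a standard deviation of 8.30) at 6 months following total knee arthroplasty". On the effect size: "A 5-point change in Oxford Knee Scores at a post-operative period of 6 months was determined to be a clinically meaningful difference". No margin is named and the sidedness of the test is not stated.
- **12.2 Data Capture and Analysis.** For the primary objective, a 95% CI for the between-group difference in 12-month OKS improvement will be computed. The section does not say what the interval must show.

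**The concern.** Superiority and comparability need different evidence. Superiority needs a CI that lies wholly above 0. Comparability needs a CI that excludes a deficit (non-inferiority), or a difference in either direction (equivalence), of a size fixed beforehand. The plan states both aims, and the one labelled primary has no criterion.

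The superiority criterion can be inferred from 3.0, 12.1 and 12.2 together. No criterion for *comparable* can be inferred from anything. If the CI contains 0, the hypothesis is not supported, but whether the primary objective has been met is left open until the results are known. The plan does not say that such a result will be called comparable. Nothing in it rules that out either, even when the interval still allows a deficit of 5 points.

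**Working it through.** **Inputs.** From 12.1: SD 8.30, difference 42 - 37 = 5, 80% power, 5% level, 45 evaluable per group (50 enrolled, because "An additional 5 patients per group (10%) has been included into the target patient number to allow for loss to follow-up"). The SD is for the attained score at 6 months. The SD of 12-month improvement, which is what 12.2 analyses, is not given, so I show in brackets the range for an assumed SD of 7 to 11. Differences are ShapeMatch minus Navigation.

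**1. The plan's own figure.** A two-sample t-test at two-sided 5% with 80% power, difference 5 and SD 8.30 needs 44.24, so 45 per group; power at 45 is 80.7%. A one-sided 5% test would need 35. The stated 45 is therefore a two-sided 5% superiority calculation.

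**2. The number alone does not settle the aim.** Non-inferiority at one-sided 2.5%, with an assumed margin of 5 and a true difference of 0, uses the same standardised distance, 5/8.30. It too gives 80.7% power at 45 per group. The superiority reading rests on the wording of 12.1, not on the arithmetic.

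**3. Width of the planned CI.**

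- SE = 8.30 × √(2/45) = 1.750
- Half-width h = t(0.975, 88 df) × SE = 1.987 × 1.750 = 3.48 (2.93 to 4.61)

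**4. Results where the ambiguity bites.** The CI contains 0 when -h < D < h. Its lower limit is below -5 when D - h < -5, that is D < h - 5. Both hold when -h < D < h - 5:

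| SD | Observed D |
|---|---|
| 7 (assumed) | -2.93 to -2.07 |
| 8.30 | -3.48 to -1.52 |
| 11 (assumed) | -4.61 to -0.39 |

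**5. How often, for assumed true differences** (noncentral t, and integration over the sample SD). No figure in the documents suggests harm; the deficits are illustrations.

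| True difference | CI contains 0 | CI contains 0 and reaches below -5 |
|---|---|---|
| 0 | 95% | 17% (6% to 41%) |
| -3 | 60% (48% to 75%) | 40% (21% to 62%) |
| -5 | 19% (8% to 43%) | 17% (6% to 41%) |

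**6. What a comparability claim would require.** The margins are assumed, since the plan gives none. True difference 0; N per group is for 80% power at SD 8.30.

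| Claim | Power at 45 per group | N per group |
|---|---|---|
| Non-inferiority, margin 5, 95% CI | 81% (57% to 92%) | 45 |
| Non-inferiority, margin 4, 95% CI | 62% (40% to 77%) | 69 |
| Non-inferiority, margin 3, 95% CI | 40% (25% to 52%) | 122 |
| Equivalence within ±5, 95% CI | 61% (14% to 84%) | 59 |
| Equivalence within ±5, 90% CI | 77% (38% to 91%) | 48 |

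**The case against.** The strongest reply is that the plan is coherent apart from one sentence. The hypothesis, the sizing and a 95% CI for the 12-month difference all fit superiority; endpoint, time point and CI level are stated; and a reader of the results would see a lower limit below -5. On this view the matter is loose wording. It could also be said that *comparable* is a minimum aim and superiority the expected result, and that the hypothesis speaks of functional outcome without naming the OKS.

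Part of this stands. The analysis can be run as written, the harm is conditional, and no passage shows an intention to report a non-significant result as comparable. The illustration should also not rest on deficits alone: with no true difference, the troublesome interval arises in 17% of trials, against 40% at a true deficit of 3.

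The rest does not remove the problem. The sentence out of line is the one labelled primary objective, and it says the trial is to demonstrate comparability. No passage sets out a hierarchy of a minimum aim and an expected result, and a minimum aim would still need a margin. The 5-point figure cannot serve as an implied margin: 12.1 gives it as a meaningful difference at 6 months, while the objective is at 12 months.

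**Conclusion.** The concern holds, and it should be resolved before the 12-month result is interpreted. Section 3.0 contradicts itself on what the main result must show, and the stated primary objective has no definition, margin or rule. The fault lies in the text: the sample size of 45 per group is correct for two-sided superiority.

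At SD 8.30 and 45 per group, observed differences from about -3.5 to -1.5 satisfy neither reading clearly: they do not show superiority, and they do not exclude a 5-point deficit. The width of this zone depends on the SD of 12-month improvement, which the plan does not give, but the zone exists across the whole assumed range of 7 to 11. The conflict between the two aims depends on no numerical assumption.

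**What to change.** Make the objective, hypothesis and decision rule state one aim.

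**Superiority (no margin, no new patients).** Reword the primary objective in 3.0 to match the hypothesis and sizing. State in 12.2 that superiority is concluded only if the two-sided 95% CI for the difference in 12-month OKS improvement (ShapeMatch minus Navigation) lies wholly above 0, and that a CI containing 0 does not by itself show comparability.

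**Comparability, if that is what the sponsor intends.** Say whether non-inferiority or equivalence is meant, justify a margin before outcome data are seen, give the CI level and the rule, and check power. The 5-point figure would need its own justification as a margin.

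Under either route, record whether 12-month outcomes had been seen when the change was made. A margin chosen afterwards must not be presented as pre-specified, and a reworded objective should be dated in the same way. Because 12.2 analyses the two- and five-year data in the same manner as the 12-month data, say whether the rule applies there too.

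**Cost.** A few sentences in 3.0 and 12.2, with the Ethics Committee approval that section 18.0 requires for any change. Superiority needs no further patients or data, but it closes off any reading of a non-significant result as comparable. For comparability at SD 8.30, non-inferiority with margin 5 fits the planned 45 per group, and margins of 4 or 3 do not. Equivalence within ±5 on a 90% CI needs 48, which is within the 50 enrolled but above the 45 left after the allowed loss; on a 95% CI it needs 59.

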7.0 STUDY DESIGN

This study will be conducted as a randomised controlled trial, designed to limit confounding bias. Participants will be recruited and assessed against the Inclusion and Exclusion criteria. If participants met these criteria they will be randomised to either the Control Group or the Intervention Group, with no other factors of influence.

This will be achieved via a block randomisation process. A central randomisation list will be computer generated by a consultant statistician. Once a patient has met criteria for enrolment, the Principal Investigator or designee will phone/email the Sponsor with the Initials, Date of Birth and Patient Number (assigned in ascending order at time of recruitment). A randomisation number, corresponding to a randomisation envelope held at the study site, will be provided. Once this number is received the envelope will be located and opened. The Principal Investigator will note the group allocation in the Case Report Form.

Patients will be blinded to their group allocation. This will allow minimal bias when completing post-operative questionnaires.

Pre- and post-operative x-rays will also be reviewed by a blinded reviewer.

Control Group - Neutral Mechanical Alignment using Navigation

Participants randomised to the Control Group will undergo Total Knee Replacement (TKR) with the goal of neutral alignment to the mechanical axis. This is the standard method for TKR with Triathlon[®] Knee System and this group will serve as a control reference for the intervention group.

Intervention Group - Kinematic Alignment using ShapeMatch®

Participants randomised to the Intervention Group will undergo TKR with the goal of kinematic alignment, re-aligning the limb to its pre-disease kinetic alignment.

Both groups will undergo treatment in parallel. The study will be conducted as a two-centre study with approximately 7 surgeons performing surgery for this study.

Patients will be followed up until 12 months post-surgery and those participating in the extension study will be followed until 5 years post-surgery.

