12.2 Data Capture and Analysis

All data will be recorded on 2-part NCR paper Case Report Forms (CRFs). The surgeon will complete and sign forms at the time of completion. Original CRFs will be collected by Stryker for data entry. Copies will remain at the Investigator site. Archiving will be undertaken in accordance with ICH/GCP guidelines (Appendix 6).

Any unclear or ambiguous data will be queried and all cleaned data will be entered into a database for tracking purposes.

The primary outcome data gathered from patients in each study group will be pooled and summarized.

For the primary objective of the study, the 95% confidence interval of the difference in total Oxford Knee Score improvement (at 12 months post-operative) between the Intervention Group and the Control Group will be computed. Two and five year data will be analysed as per the 12 month data.

For secondary objectives, independent two-sample t-test or Wilcoxon non-parametric rank-sum test will be used to compare the International Knee Society Score (IKSS), Forgotten Joint Score (FJS), WOMAC, EQ-5D and VAS Pain scores between the Intervention Group and the Control Group at all available visits. Please note that the test we intend on using will be dependent on the distribution of the data collected following appropriate normality testing. Adjustments will be made for multiple testing at each level.

Independent two-sample t-test or Wilcoxon non-parametric rank-sum test will also be used to compare cost-effectiveness and cost-utility between the Intervention Group and the Control Group. As mentioned above, this will also be dependent on the distribution of the data collected.

Adverse events will be tabulated separately and reviewed for any commonalities. Revision surgery data from the Extension Study will be compared to the revision rates reported in the National Joint Registry report at 2 years and 5 years. A cost benefit analysis will be undertaken with the use of data from the Australian Government Hospital Casemix Protocol Annual Report.

A formal interim analysis will take place following completion of the ShapeNZRCT-10 study (12 month visit). Additionally, formal interim analyses will take place following all participants' completion of the 2 year visit and again following completion of all participants' 5 year follow-up visits.

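### The QALY comparison is undefined in form and unadjusted for pre-operative EQ-5D-3L; adjusting would cost nothing and could gain precision, by an amount that depends on a correlation the plan does not give

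*Combined protocol and SAP*

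**What the plan says.** Section 3.0 makes cost-effectiveness and cost-utility a secondary objective. The last of its five listed parameters is "Quality-adjusted life-years (QALYs) from EQ-5D-3L". Sections 3.0, 11.0 and 12.2 do not say how a QALY is formed from the questionnaire, or what part the pre-operative value plays.

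EQ-5D-3L is among the secondary measures to be obtained by "utilizing the following instruments pre-operatively and at the 6-week, 6-month and 12 month visits". The evaluation schedule in section 1.0 agrees: it is ticked pre-operatively and at 6 weeks, 6 months and 12 months for all patients. The pre-operative window is "Pre-Op = Within 2 months before the date of surgery", so that value precedes treatment.

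The analysis is in section 12.2: "Independent two-sample t-test or Wilcoxon non-parametric rank-sum test will also be used to compare cost-effectiveness and cost-utility". The choice between the two tests rests on distribution alone: "As mentioned above, this will also be dependent on the distribution of the data collected". The only adjustment mentioned in 12.2 is for multiple testing. The Oxford Knee Score is analysed as improvement, so it takes account of the starting level; nothing comparable is stated for EQ-5D or QALYs.

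Section 7.0 describes block randomisation in which patients are "randomised to either the Control Group or the Intervention Group, with no other factors of influence". Baseline utility is therefore balanced by chance only.

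**The concern.** A patient's QALYs over the year after surgery are likely to depend on utility before surgery. If they are computed as an area under the utility curve, the pre-operative value is the first point of that area, and it may also predict the later points. A comparison that ignores it leaves explainable variation in the standard error. In a trial of 50 per arm, it also leaves the estimate exposed to whatever difference in pre-operative utility chance produces.

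The sample size in 12.1 is set on the Oxford Knee Score, so precision for the economic outcome is whatever the analysis can extract. Leaving the adjustment unstated also leaves room to choose between adjusted and unadjusted results once the baseline table has been seen.

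**Working it through.** **The plan's own figure.** The documents give no SD, expected difference or sample size for EQ-5D or QALYs. The only calculation is for the Oxford Knee Score (12.1). For a difference of 5, SD 8.30, two-sided 5% and 80% power, the normal formula gives 44 per arm and the t-test version 44.2, rounded up to 45. Then 45/0.9 = 50. The stated 45 and 50 reproduce, and 50 per arm is used below.

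**Inputs.**
- Visit times 0, 6/52, 0.5 and 1 year, from the schedule in section 1.0, taking the pre-operative value as time 0.
- QALY as a trapezoidal area: an assumption, being the usual method.
- Pre-operative utility SD (s) 0.20 to 0.30, later SD 0.8s, correlation 0.6 among the three follow-up visits, pre/post correlation r from 0 to 0.5: all assumed, since the documents give none.

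**Weights.** Each point gets half the length of its adjoining intervals (0.1154, 0.3846 and 0.5 year):
- pre-operative: 0.1154/2 = 0.058
- 6 weeks: (0.1154 + 0.3846)/2 = 0.250
- 6 months: (0.3846 + 0.5)/2 = 0.442
- 12 months: 0.5/2 = 0.250

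**Slope of QALY on baseline.** b = 0.058 + 0.942 × 0.8 × r.

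**SD of the QALY, in units of s.** The three follow-up weights have sum of squares 0.3206, and the square of their sum is 0.8879. Their variance contribution is 0.64 × [0.3206 + 0.6 × (0.8879 − 0.3206)] = 0.4230. The baseline adds 0.0577² = 0.0033, and the covariance adds 2 × 0.0577 × 0.9423 × 0.8 × r = 0.0870r. So the variance is 0.4264 + 0.0870r.

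**Effect of a one-standard-error imbalance.** The imbalance is s√(2/50) = 0.2s. It shifts the QALY difference by b × 0.2s, while the unadjusted standard error is SD × 0.2s. The ratio is b/SD, which depends on neither s nor the number per arm. Adjustment multiplies the standard error by √(1 − R²), with R² = (b/SD)². This ignores the small cost of estimating one slope.

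| r | b | SD (units of s) | shift ÷ SE | R² | SE multiplier | cut in SE |
|---|---|---|---|---|---|---|
| 0 | 0.058 | 0.653 | 0.09 | 0.008 | 0.996 | under 1% |
| 0.2 | 0.208 | 0.666 | 0.31 | 0.098 | 0.950 | 5% |
| 0.5 | 0.435 | 0.685 | 0.63 | 0.402 | 0.773 | 23% |

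**In QALYs.** A one-standard-error imbalance is 0.04 (s = 0.20) to 0.06 (s = 0.30). The shift is 0.0023 to 0.0035 at r = 0. At r = 0.2 and s = 0.20 it is 0.208 × 0.04 = 0.008; at r = 0.5 and s = 0.30 it is 0.435 × 0.06 = 0.026. The standard error falls from 0.0266 to 0.0253 in the first of these two cases and from 0.0411 to 0.0318 in the second.

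**Direct and indirect parts.** The direct weight accounts for 0.058/0.208 = 28% of the slope at r = 0.2 and 0.058/0.435 = 13% at r = 0.5. The rest, 72% to 87%, is ordinary prognostic correlation.

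**The case against.** Randomisation protects the planned comparison. Its standard error already includes chance variation in pre-operative utility, and type I error is not inflated. This stands in full. A reader might infer that the unadjusted test is biased or invalid; the documents do not support that. What remains is conditional: given an observed imbalance, the unadjusted estimate is expected to be off in a known direction.

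The direct weight of the pre-operative value is about 6%, so it is tempting but wrong to say that the QALY is driven by its starting point. Most of the effect needs a pre/post correlation that the documents do not give, and if it is zero, adjustment gains nothing useful. This also stands. The same prognostic argument applies to the other secondary scores that are measured pre-operatively and compared unadjusted.

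The area-under-the-curve form is an inference. A QALY gain with the baseline level subtracted is not ruled out, and the slopes above would not apply to it: over one year the slope becomes b − 1, that is −0.942 at r = 0 and −0.565 at r = 0.5. This objection stands against the figures but not against the remedy. Subtracting the baseline changes only the covariate's coefficient, so the regression gives the same arm difference under either definition. The unadjusted comparison does not.

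**Conclusion.** The point holds as an improvement in precision and pre-specification for one secondary economic outcome. The QALY has no stated formula, and its comparison ignores a covariate the trial already schedules for everyone. Under the assumptions above, the cut in standard error runs from negligible (r = 0) through 5% (r = 0.2) to 23% (r = 0.5), and a one-standard-error imbalance moves the estimate by about 0.09, 0.31 and 0.63 of its standard error. Where the trial falls in that range cannot be told from the documents.

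A reader might also conclude that such shifts are large beside the true difference between the techniques. The plan states no expected QALY or EQ-5D difference, so that comparison cannot be made. The primary Oxford Knee Score analysis and the sample size are unaffected.

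**What to change.** In section 12.2, replace the t-test or rank-sum comparison for QALYs with wording to this effect: 12-month QALYs are the trapezoidal area under EQ-5D-3L utility from the pre-operative, 6-week, 6-month and 12-month assessments; the difference between arms is estimated by linear regression of QALY on arm with pre-operative EQ-5D-3L utility as covariate, and reported with a 95% confidence interval, by bootstrap if residuals are skewed; this adjusted difference is the one used in the cost-utility result.

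The cost is one or two sentences. The covariate is already scheduled, and no extra patients, visits or data are needed.
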